#### 14.1.4 Demographic Data

Population: Intent-to-Treat Population

Characteristics	Treatment Group	P-value
. Study Site		
N (Missing)	XXX (XXX)	
001-CARE	XXX (XXX.X%)	
002-CAR	XXX (XXX.X%)	
. Repeat Variable:		
Age [Y/O], Baseline Body Weight [kg], Body Height [cm],		
Baseline BMI [kg/m^2]	T/W	
N (Missing)	XXX (XXX)	0.XXXX
Mean (SD)	XXX (XXX)	
Median (IQR)	XXX (XXX)	
Q1~Q3	XXX~XXX	
Min~Max	XXX~XXX	
. Gender	C/F	
N (Missing)	XXX (XXX)	0.XXXX
Male	XXX (XXX.X%)	
Female	XXX (XXX.X%)	
. Race		
N (Missing)	XXX (XXX)	
Black /African American	XXX (XXX.X%)	
American Indian or Alaska Native	XXX (XXX.X%)	
Asian	XXX (XXX.X%)	
Native Hawaiian or Other Pacific Islander	XXX (XXX.X%)	
White	XXX (XXX.X%)	
...		
. Ethnicity	C/F	
N (Missing)	XXX (XXX)	0.XXXX
Hispanic or Latino	XXX (XXX.X%)	
Not Hispanic or Latino	XXX (XXX.X%)	
...		

Age [years old]=(Date of informed consent obtained – birth date)/365.25 rounded down to the nearest integer

BMI [kg/m^2]= Weight [kg] / (Height [cm])^2 \* 10000

Baseline is Visit 2 or alternatively as Visit 1 if Visit 2 data is not available.

### 14.1.5 Coronavirus Disease 2019 (COVID-19) History

Population: Intent-to-Treat Population

Characteristics	Treatment Group	P-value
. Repeat Variable:		
Disease Duration [days],		
Symptom Duration [days],		
Symptom Duration up to Randomization [days]		TW
N (Missing)	XXX (XXX)	0.XXXX
Mean (SD)	XXX (XXX)	
Median (IQR)	XXX (XXX)	
Q1~Q3	XXX~XXX	
Min~Max	XXX~XXX	
. COVID-19 Vaccination History		
N	XXX	
At least one below [Event#:Subj#]	XXX : XXX (XXX.X%)	
~ AstraZeneca	XXX : XXX (XXX.X%)	
~ Johnson & Johnson	XXX : XXX (XXX.X%)	
~ Pfizer	XXX : XXX (XXX.X%)	
~ Moderna	XXX : XXX (XXX.X%)	
...	...	

Disease Duration [days] =(date of screening visit – date of first positive RT-PCR for testing COVID-19),  
 Symptom Duration [days] =(date of screening visit – start date of COVID-19 self-reported by patient),  
 missing day is estimated as 15, missing month is estimated as Jul-01, full unknown is missing

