4. STUDY DESIGN

4.1. OVERALL DESIGN

This is a phase II multicenter, randomized, open-label, 2 arm parallel-group controlled interventional prospective study of CX-4945 in patients with COVID-19. Up to approximately 20 patients will be enrolled into this study. A screening evaluation will occur within 7 days prior to Day 1. At the end of screening all qualified patients will be randomized in a ratio of 1:1 to one of the following two treatment arms:

- **Arm A:** the best supportive and/or standard of care in combination with CX-4945 1000 mg BID PO or
- **Arm B:** the best supportive/standard of care

The **best supportive care** is defined as intensive care therapy according to current guidelines, evidence, and best practice, including but not limited to lung protective ventilation, thrombosis prophylaxis, renal replacement therapy when indicated, and access to advanced therapies including extracorporeal membrane oxygenation.

The **standard of care (SOC)** is not pre-specified and may vary among patients, and may include agents with anti-viral activity, such as remdesivir, among others. Investigator discretion is to be applied for any established SOC. Patients progressed on treatment with monoclonal antibodies can be enrolled, if meet eligibility criteria. Active concomitant treatment with other investigational antivirals or immunomodulators are not permitted.

Patients assigned to Arm B will do all the same assessments as Arm A.

The total duration of the treatment will be 14 days. Patients will be followed up at 28, 45 and 60 days from the start of the treatment. The total duration for each patient in the study (including the screening) will be up to 67 days. For details on randomization see **Section 6.1.2**.

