5.1.1. Inclusion Criteria

Patients must meet all of the following inclusion criteria to be eligible for enrollment in the study:

1. Male or non-pregnant female adult ≥ 18 years of age
2. Diagnosed with COVID-19 by standard RT-PCR assay within 7 days prior to randomization (Day 1)
3. Outpatients with moderate illness caused by SARS-CoV-2 infection as defined below,
 - Symptoms of moderate systemic illness/infection with COVID-19:
 - At least two of the key **COVID-19-related** symptoms with score 2 or higher: cough, sore throat, stuffy or runny nose, shortness of breath, feeling of tightness of chest, feeling of fast heartbeat, low energy or tiredness, muscle cramps, joint pain, chills or shivering, feeling hot or feverish, difficulty in concentration (brain fog), sleep disturbances, headache, dizziness, anxiety, feeling of tingling, nausea (*scoring values: None = 0; Mild = 1; Moderate = 2; and Severe = 3*), vomiting, diarrhea (*scoring values: Not at all = 0; 1–2 times = 1; 3–4 times = 2; 5 or more times = 3*), loss of taste or smell (*scoring values: The same as usual = 0, Less than usual = 1, NO sense of smell/taste = 2*)

AND

- Clinical signs indicative of moderate systemic illness/infection with COVID-19
 - At least one of the following:
 - Respiratory rate ≥ 20 breaths per minute
 - Heart rate ≥ 90 beats per minute

AND

- No clinical signs indicative of severe or critical illness severity required hospitalization (see exclusion criterion #1)
- 4. Patient (or legally authorized representative) provides written informed consent prior to initiation of any study procedures.
- 5. Adequate hematopoietic capacity, as defined by the following:
 - a. Hemoglobin \geq 9.0 g/dL and not transfusion dependent
 - b. Platelets \geq 100,000/mm³
 - c. Absolute neutrophil count \geq 1500 cells/mm³
- 6. Adequate hepatic function, as defined by the following:
 - a. AST and ALT \leq 2.5 times upper limit of normal (ULN)
 - b. Total bilirubin \leq 1.5 x ULN
 - c. Albumin \geq 3.0 g/dL
- 7. Adequate renal function, as defined by the following:
 - a. Renal: calculated creatinine clearance >45 mL/min for patients with abnormal, increased creatinine levels (Cockcroft-Gault formula).
- 8. Ability to take oral medication and be willing to adhere to drug administration and premedication requirements (see **Section 6.3**) throughout the study duration.

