## 2 Protocol Versions and Protocol Amendments

The first subject was enrolled on 3-Dec-2020, and the last subject is expected to be dismissed on 7-Oct-2021. All applied protocol and CRF versions are listed as below.

No.	Protocol Version	CRF Version	IRB Approval	FDA Approval
1	3.0, 20OCT2020	1.1, 12OCT2021	5-Nov-2020	3-Nov-2020
2	Amendment 1.0, 11MAY2021	1.0, 06SEP2021	24-May-2021	24-Jun-2021

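### Partial COVID-19 start dates are set to day 15 or 1 July with no bound at screening, so baseline symptom duration can come out negative or, when the month is missing, months long

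*SAP*

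**What the plan says.** SAP 14.1.5 tabulates three baseline durations by arm, with a t test or Wilcoxon p-value. Disease duration runs to screening from the "date of first positive RT-PCR for testing COVID-19". Symptom duration runs to screening from the "start date of COVID-19 self-reported by patient". The third, symptom duration up to randomization, has no formula of its own. The footnote then gives the partial-date rule: "missing day is estimated as 15, missing month is estimated as Jul-01, full unknown is missing".

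Neither document caps the imputed date at screening or randomization, sets an earliest allowed date, or says what to do with a negative result.

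The trial's timing comes from four places:
- SAP section 2: "The first subject was enrolled on 3-Dec-2020, and the last subject is expected to be dismissed on 7-Oct-2021".
- Protocol 4.1: "A screening evaluation will occur within 7 days prior to Day 1".
- Protocol 5.1.1, criterion 2: RT-PCR diagnosis within 7 days before randomization.
- Protocol 5.1.1, criterion 3: at least two key symptoms scored 2 or higher.

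No criterion in 5.1.1 or 5.1.2 limits the time since symptom onset.

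**The concern.** Mid-month and mid-year substitution is designed for histories measured in months or years, where an error of two weeks or half a year matters little. Here patients are diagnosed within a week of randomization and already have symptoms, so durations are probably counted in days. A negative symptom duration says that symptoms began after screening, which is impossible for a patient who was symptomatic at entry.

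The footnote contains two separate faults. The missing-day rule has no upper bound at screening, so it can give negative values. The missing-month rule shares that fault and also has no earliest date, so it can give values of several months.

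What is at stake is the description of the two arms. Time since onset is a natural thing to compare at baseline in a small open-label COVID-19 trial, and with about 10 patients per arm one impossible value can make the mean and SD meaningless.

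**Working it through.** The plan states no figure to reproduce, so the check applies its rule to its own calendar.

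**Inputs**
- First subject enrolled 3 December 2020; last expected out 7 October 2021 (SAP section 2). If the last visit is Day 60, the last Day 1 is 59 days earlier, 9 August 2021 (6 to 12 August with the ±3-day window).
- Screening dates used: every day from 3 December 2020 to 9 August 2021, 250 dates.
- About 20 patients randomized 1:1 (Protocol 9.3), so about 10 per arm.
- Assumption: true onset is T days before screening. The documents give no value. T = 3, 5, 7 and 10 is used for the missing day, and T = 1 to 14 for the missing month.

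**Missing day.** Imputed duration = screening date minus the 15th of the onset month. Let d be the day of the month of screening. Onset falls in the same month when d ≥ T + 1. The imputed duration is then d - 15, which is negative when d ≤ 14. Each full month therefore has 14 - T negative dates. December (from the 3rd) also has 14 - T for these values of T, January to July have 7 × (14 - T), and 1 to 9 August have 9 - T, or none if T ≥ 9.

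| T (days) | Dec | Jan-Jul | Aug | Total | Share of 250 |
|---|---|---|---|---|---|
| 3 | 11 | 77 | 6 | 94 | 37.6% |
| 5 | 9 | 63 | 4 | 76 | 30.4% |
| 7 | 7 | 49 | 2 | 58 | 23.2% |
| 10 | 4 | 28 | 0 | 32 | 12.8% |

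The imputed values run from T - 14 to T + 16, so from -11 (T = 3) to +26 (T = 10). The mean absolute error is 7.7 to 7.8 days for each of these gaps.

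**Missing month.** Imputed duration = screening date minus 1 July of the onset year.
- 3 December 2020 minus 1 July 2020: 30 + 31 + 30 + 31 + 30 + 3 = +155 days.
- 10 March 2021 minus 1 July 2021: -(21 + 30 + 31 + 30 + 1) = -113 days.
- Negative results: onset in 2021 and screening before 1 July 2021, which is 181 - T dates. This is 180/250 = 72% at T = 1 and 167/250 = 67% at T = 14. The lowest value is -180 (2 January 2021, T = 1).
- Results of 60 days or more: onset in 2020, which is 29 + T dates. This is 30/250 = 12% at T = 1 and 43/250 = 17% at T = 14. The highest value is 183 + 14 = +197.
- Results of 0 to 14 days: only screenings on 1 to 15 July 2021, 15/250 = 6%.

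**Effect on an arm of 10.** Take nine patients at 5 days plus one imputed value, against a true mean of 5.
- +155: mean (45 + 155)/10 = 20.0; SD √[(9 × 15² + 135²)/9] = 47.
- -113: mean (45 - 113)/10 = -6.8; SD √[(9 × 11.8² + 106.2²)/9] = 37.
- Missing day, extremes at T = 5 (-9 and +21): the mean moves by (-9 - 5)/10 = -1.4 or (21 - 5)/10 = +1.6 days.

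**Effect on the median and the test.** In 2,000 simulated arms of 10 for each value, with assumed true durations of 2 to 10 days and one value replaced by +155 or -113, Shapiro-Wilk rejected normality every time. SAP 3.1 then calls for the Wilcoxon test. The median moved by about 0.4 days on average and by at most 3.5.

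**The case against.** The strongest reply is that this may never happen. Patients are asked at screening about an illness that probably began days earlier, and neither document says how many start dates will be partial. A known year with an unknown month is the only route to the months-long values, and it is an unlikely answer for so recent an onset. This stands. The percentages above are shares of screening dates given that a date is partial. A reader might take them as shares of patients, and the documents do not support that.

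The SAP also contains safeguards. The switch in 3.1 makes the comparison rank-based, so the size of an outlier no longer drives the p-value. The table also shows median, IQR and range, and Protocol 9.7 has all data listed, so an impossible value would be visible. This stands for the median and p-value. It does not rescue the mean, SD, minimum or maximum, which would still be reported as baseline facts.

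A reader might infer that this table is the only check on illness stage, because entry has no limit on time since onset. The documents do not bear that out. The table is descriptive and controls nothing. Disease duration from first positive RT-PCR appears beside it, and criterion 2 makes a partial date there unlikely. Nor does the imputation error always exceed the duration being measured: at an assumed gap of 10 days, a mean error of about 7.7 days is smaller. The missing-day rule never gives a months-long value for a recent onset.

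**Conclusion.** The point holds as a minor one. The footnote, followed as written, can produce impossible durations in this trial's calendar. If the day is missing, between 13% and 38% of screening dates give a negative duration for assumed onset gaps of 10 down to 3 days. If the month is missing, only 6% of screening dates give a value between 0 and 14 days.

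The result rests on the assumed onset gaps, on evenly spread screening dates, and on partial dates occurring at all. If none occur, the effect is zero.

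It would be tempting to read this as a threat to the trial's results, but the documents do not support that. The primary endpoint is adverse events. Time to response counts from first treatment, or from Visit 2 in the control arm (SAP 1.4.2). The ANCOVA covariate is the baseline laboratory or vital-sign value (SAP 1.4.3), and no model in the SAP uses symptom duration. The damage is limited to the baseline symptom-duration summaries.

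**What to change.** Replace the partial-date footnote in SAP 14.1.5 with three rules:
- If only the day is missing, impute the midpoint between the first of the stated month and the earlier of that month's end and the screening date.
- If the month is missing, leave the duration missing, as the SAP already does for a fully unknown date.
- Flag every imputed date in the patient listing.

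On the same 250 dates, the midpoint rule (rounded down to whole days) gives no negative values and lowers the mean absolute error from about 7.7 days to 5.3-6.2 days for gaps of 3 to 10 days. A cap at screening alone is not enough, because the missing-month rule would still give up to 197 days.

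Do not also cap onset at the first positive RT-PCR. The documents do not say that symptoms always precede the test, and the window can become empty: with a test on 30 January and onset recorded as February, it would have to start on 1 February and end on 30 January.

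The cost is one footnote or code change and possibly a few more missing values.

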### 14.1.6 General Medical History and Concurrent Disease/Status

Population: Intent-to-Treat Population

Characteristics	Treatment Group
. General Medical History	
N	XXX
At least one below	XXX (XXX.X%)
~ <Body System 1>	XXX (XXX.X%)
~ <Body System 2>	XXX (XXX.X%)
~ <Body System 3>	XXX (XXX.X%)
~ <Body System 4>	XXX (XXX.X%)
...	...
. Current Condition (Multi-Selection)	
N	XXX
At least one below	XXX (XXX.X%)
~ <Body System 1>	XXX (XXX.X%)
~ <Body System 2>	XXX (XXX.X%)
~ <Body System 3>	XXX (XXX.X%)
~ <Body System 4>	XXX (XXX.X%)
...	...

Current condition lists the medical histories that are ongoing or with end date  $\geq$  date of visit 2

### 14.1.7 Concomitant Medications

Population: Intent-to-Treat Population / Safety Population

Characteristics	Treatment Group
--Repeat Population: <See populations above>	
Repeat Variable: Prior Medication, Concomitant Medication (Multi-Selection by Highest ATC Level Class and ATC Preferred Term)	
N	XXX
At least one below	XXX (XXX.X%)
~ <Highest ATC Level Class 1>	XXX (XXX.X%)
~ <ATC Preferred Term 1>	XXX (XXX.X%)
~ <ATC Preferred Term 2>	XXX (XXX.X%)
...	...
~ <Highest ATC Level Class 2>	XXX (XXX.X%)
~ <ATC Preferred Term 1>	XXX (XXX.X%)
~ <ATC Preferred Term 2>	XXX (XXX.X%)
...	...

WHODrug Global B3-format September 1, 2020 is used for coding

Prior Medication: medications onset prior to Day 1

Concomitant Medication: medications applied on / after Day 1

### 14.1.8 Best Supportive / Standard Of Care Procedures

Population: Intent-to-Treat Population

Characteristics	Treatment Group	P-value
- Repeat Duration: Prior Procedure, Concomitant Procedure, Post Procedure		
. Repeat Variable: Subject with Best Supportive / Standard Of Care Procedures (Multi-Selection by Highest ATC Level Class and ATC Preferred Term)		
N	XXX	C/F
At least one below [Day#:Subj#]	XXX : XXX (XXX.X%)	0.XXXX
Extracorporeal Membrane oxygenation	XXX : XXX (XXX.X%)	0.XXXX
Fluid management	XXX : XXX (XXX.X%)	0.XXXX
Mechanical Ventilation	XXX : XXX (XXX.X%)	0.XXXX
~ High-flow oxygen	XXX : XXX (XXX.X%)	0.XXXX
~ Supplemental oxygen	XXX : XXX (XXX.X%)	0.XXXX
~ Noninvasive ventilation	XXX : XXX (XXX.X%)	0.XXXX
~ Extracorporeal membrane oxygenation (ECMO)	XXX : XXX (XXX.X%)	0.XXXX
~ Other	XXX : XXX (XXX.X%)	0.XXXX
Prone position	XXX : XXX (XXX.X%)	0.XXXX
. Days with Mechanical Ventilation [days]		TW
N (Missing)	XXX (XXX)	0.XXXX
Mean (SD)	XXX (XXX)	
Median (IQR)	XXX (XXX)	
Q1~Q3	XXX~XXX	
Min~Max	XXX~XXX	

Prior Procedure: procedures onset prior to Day 1

Concomitant Procedures: procedures from Day 1 to End of Treatment Visit

Post Procedure: procedures after End of Treatment Visit to End of Study

Day# = End date/time – Start date/time, rounded up to the nearest integer

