	To evaluate other Clinical Benefit of treatment with CX-4945 relative to the control arm	
• All-cause mortality status – the number of deaths occurred in each treatment group from Randomization (Day 1) through Day 60.• Number of respiratory failure (i.e., need for mechanical ventilation, ECMO, noninvasive ventilation, or high-flow nasal cannula oxygen delivery) occurred in each treatment group from Randomization (Day 1) through Day 45.• Number of patients hospitalized in each treatment arm from Randomization (Day 1) to Day 45• Number of days to normalization of oxygen saturation level measured by pulse oximeter at Randomization (Day 1), Day 4, Day 8, Day 11, Day 14, Day 28 and Day 45 and categorized as <96% versus ≥96%. Proportion of patients with disease progression or improvement in health status occurring from Randomization (Day 1) to Day 28. Disease progression is defined as change in patient health status assessment from item 7 to items 1- 6 and health improvement -as change from item 7 to item 8, evaluated by the ordinal NIAID 8-Point Clinical Progression Outcomes scale collected at every visit from Day 1 through Day 45. 
The 8-category ordinal scale of patient health status ranges from:
 
1. Death;2. Hospitalized, on invasive mechanical ventilation or extracorporeal membrane oxygenation (ECMO);

		
3. Hospitalized, on non-invasive ventilation or high flow oxygen devices;4. Hospitalized, requiring supplemental oxygen;5. Hospitalized, not requiring supplemental oxygen - requiring ongoing medical care (COVID-19 related or otherwise);6. Hospitalized, not requiring supplemental oxygen - no longer requires ongoing medical care;7. Not hospitalized, limitation on activities and/or requiring home oxygen;8. Not hospitalized, no limitations on activities. 
• Changes in EQ-D5-5L (used as an indicator of symptom improvement) from randomization (Day 1) to Day 8, Day 14 and Day 28.
	To evaluate changes in inflammatory markers	
• Changes in plasma IL-6 level from randomization (Day 1) to Day 4, 8, 11, and 14.• Changes in CRP, LDH, CPK, ferritin, D-dimer from randomization (Day 1) to Day 4, 8, 11, and 14.

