5.1.2. Exclusion Criteria

Potential patients meeting any of the following criteria will be excluded from participation in this study:

1. Any signs indicative of severe or critical illness severity required hospitalization as defined below:
 - Severe COVID-19: Shortness of breath at rest, or respiratory distress, respiratory rate (RR) \geq 30 per minute, heart rate (HR) \geq 125 bpm, SpO₂ \leq 93% on room air at sea level or PaO₂/FiO₂ $<$ 300
 - Critical COVID-19: Respiratory failure required mechanical ventilation, oxygen delivered by high-flow nasal cannula, ESMO; shock or multi-organ dysfunction/failure

2. Pregnant or nursing women.

NOTE: Women of child-bearing potential and men must agree to use adequate contraception (hormonal or barrier method of birth control; or abstinence) prior to study entry and for the duration of study participation. Should a man father a child, or a woman become pregnant or suspect she is pregnant while participating in this study, he or she should inform the treating physician immediately.

3. Active or uncontrolled infections other than COVID-19 or with serious illnesses or medical conditions which would not permit the patient to receive study treatment
4. Chronic diarrhea (excess of 2-3 stools/day above normal frequency)
5. Concomitant treatment with another investigational drug
6. Current use or anticipated need for drugs that are known strong inhibitors or inducers of major CYP enzymes.
7. Any active or recurring clinically significant hepatic disease.

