## 14.2.4 Clinical Status - NIAID 8-Point Clinical Progression Outcomes Scale

### 14.2.4.1 Clinical Status - NIAID 8-Point Clinical Progression Outcomes Scale

Population: Intent-to-Treat Population / Per-Protocol Population

Characteristics	Treatment Group	P-value
--Repeat Population: <See populations above>		
N	XXX	
Subjects with any below [Event#:Subj#]	XXX : XXX (XXX.X%)	
~ Death (NIAID item 1)	XXX : XXX (XXX.X%)	
~ Respiratory Failure (NIAID item 2~3 or from AE)	XXX : XXX (XXX.X%)	
~ Hospitalized (NIAID item 2~6)	XXX : XXX (XXX.X%)	
. Repeat Visit: No 'Visit 1 (Screening)' for IL-6: Visit 1 (Screening), Baseline, Adjusted Visit 3 (Day 4), Adjusted Visit 4 (Day 8), Adjusted Visit 5 (Day 11), Adjusted Visit 6 (Day 14, EOT), Visit 7 (Day 28, F1), Visit 8 (Day 45, F2), LOCF		
N (Missing)	XXX (XXX)	0.XXXX
Item 1	XXX (XXX.X%)	
Item 2	XXX (XXX.X%)	
...	...	
Item 8	XXX (XXX.X%)	
Repeat [Baseline to Visit] except Visit 1 (Screening), Baseline		
N (Missing)	XXX (XXX)	C/F
Improvement (Item 7 to Item 8)	XXX (XX.X%)	0.X
Progression (Item 7 to Item 1~6)	XXX (XX.X%)	XX
		X

Respiratory failure required mechanical ventilation, oxygen delivered by high-flow nasal cannula, ESMO; shock or multi-organ dysfunction/failure

For NIAID 8-Point Clinical Progression Outcomes Scale:

Item 1 - Death

Item 2~3 - Hospitalized, respiratory failure

Item 4~6 - Hospitalized, non-respiratory failure

Item 7 - Not hospitalized, limitation on activities and/or requiring home oxygen

Item 8 - Not hospitalized, no limitations on activities

Refer to [Instructions and Abbreviations] of title pages for further definition

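### SAP Table 14.1.8 counts oxygen therapy under mechanical ventilation, and the adverse-event route to respiratory failure in 14.2.4.1 can admit shock or organ failure without ventilatory support

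*SAP*

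**What the plan says.** **SAP 14.1.8 (care procedures).** Under the parent row Mechanical Ventilation the shell indents five sub-rows: high-flow oxygen, "Supplemental oxygen", non-invasive ventilation, ECMO and other. ECMO also has its own top-level row. Each row reports days and subjects together and has a p-value. A further variable, "Days with Mechanical Ventilation [days", is compared between arms by t test or Wilcoxon test. The footnote defines the day count as end minus start, rounded up, but does not say which sub-rows supply the days.

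**SAP 14.2.4.1 (clinical status).** The counting row reads "Respiratory Failure (NIAID item 2~3 or from AE". The footnote says: "Respiratory failure required mechanical ventilation, oxygen delivered by high-flow nasal cannula, ESMO; shock or multi-organ dysfunction/failure". The scale key below it calls items 2 and 3 respiratory failure and items 4 to 6 non-respiratory failure.

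**Protocol.** The Synopsis (1.1) gives the endpoint as "Number of respiratory failure (i.e., need for mechanical ventilation, ECMO, noninvasive ventilation, or high-flow nasal cannula oxygen delivery", counted from Day 1 through Day 45. Section 3 lists the other clinical-benefit endpoints but not this one. The SAP footnote's wording comes from exclusion criterion 1 in 5.1.2, where it carries a label that the SAP drops: "Critical COVID-19: Respiratory failure required mechanical ventilation".

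**The concern.** The protocol's eight-point scale treats the levels of support as different states. Invasive ventilation or ECMO is item 2, non-invasive ventilation or high-flow oxygen is item 3, supplemental oxygen in hospital is item 4, and home oxygen falls within item 7. Table 14.1.8 puts several of these under one label, the name of the most severe. A patient on low-flow oxygen could then be reported as mechanically ventilated, and the finished table would not show how many patients were invasively ventilated, because no sub-row is named for that.

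In 14.2.4.1 the issue is which adverse events qualify. The footnote is the only text that could tell a programmer, and it describes a wider clinical state than the endpoint: it adds shock and multi-organ failure and does not name non-invasive ventilation. At stake is whether the count reported for a synopsis secondary endpoint is the count the protocol defines.

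**Working it through.** The plan states no figure on this point and has no power calculation (Protocol 9.3), so there is nothing to reproduce. The check compares the texts and then sizes the effect.

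**1. What the indentation means.** Elsewhere in the SAP the '~' mark denotes a subset of the row above. In 14.1.3 each follow-up visit is split into in-person and remote; in 14.3.1.1 subjects with an adverse event are split by grade. Applied to 14.1.8, a patient with supplemental oxygen alone counts in the Mechanical Ventilation row. Because that row reports days as well as subjects, the oxygen days can go with the patient. For the separate days variable no rule is given, so pooling is a natural reading but not a stated one.

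**2. Respiratory failure: endpoint against counting rule.**

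| Condition | Synopsis endpoint | SAP scale items 2 and 3 | SAP footnote |
|---|---|---|---|
| Invasive mechanical ventilation | yes | yes (item 2) | yes |
| ECMO | yes | yes (item 2) | yes (spelled ESMO) |
| Non-invasive ventilation | yes | yes (item 3) | not named |
| High-flow oxygen | yes | yes (item 3) | yes |
| Shock | no | no | yes |
| Multi-organ dysfunction or failure | no | no | yes |

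The scale route agrees with the endpoint. The difference can arise only through the adverse-event route read with the footnote. Protocol 6.1.5 also lists respiratory failure, shock and organ failure as separate entries.

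**3. Why the adverse-event route matters.** The scale is collected at visits, and no visit is scheduled between Day 14 and Day 28 or between Day 28 and Day 45. An episode that starts and ends in one of those gaps may reach the count only as an adverse event.

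**4. Size.** Inputs: approximately 20 patients randomized 1:1 (Protocol 9.3), so an assumed 20/2 = 10 per arm.

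- One reclassified patient: 1/10 = 10 percentage points.
- Hypothetical example for 14.1.8: one patient with 10 days of supplemental oxygen and no ventilation gives 1/10 = 10% in the Mechanical Ventilation row, and 10 days if the sub-rows are pooled. With oxygen kept separate, both figures are 0.
- Test used: with t events in total, the expected counts are t/2 and (20 − t)/2. The SAP's rule (section 3.2) allows chi-square in a 2×2 table only if all four are at least 5, which requires t = 10. Otherwise Fisher's exact test applies.
- Two-sided Fisher p for 0/10 against k/10 is 2 × C(10,k)/C(20,k):
  - k = 1: 2 × 10/20 = 1.00
  - k = 2: 2 × 45/190 = 0.47
  - k = 3: 2 × 120/1140 = 0.21
  - k = 4: 2 × 210/4845 = 0.087
  - k = 5: 2 × 252/15504 = 0.033

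These p-values bear on 14.1.8, whose rows are tested. The 14.2.4.1 shell shows no p-value against the respiratory-failure row, so there the effect is on the reported count.

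**The case against.** The best case for the SAP has four parts.

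- **14.1.8 is descriptive.** It sits with demographic and baseline tables, and neither a mechanical-ventilation row nor ventilation days is a protocol endpoint. Supplemental oxygen has its own sub-row, so a careful reader can see part of what makes up the parent. This stands and limits the harm, but the parent row and the days are still tested under a misleading label.
- **The main counting rule is right.** Items 2 and 3 are the endpoint's four supports. This stands in full.
- **The footnote may be a misplaced list.** It does not say that it defines the row, and a semicolon separates respiratory failure from shock. That is fair, so the text supports saying that such events can be counted, not that they will be. But nothing else says which adverse events qualify.
- **Non-invasive ventilation is covered elsewhere.** Item 3 captures it in hospital, and 14.1.8 files it under mechanical ventilation, which the footnote does name. This mostly stands; the gap is limited to the adverse-event route.

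A reader might infer that low-flow oxygen inflates the respiratory-failure endpoint. The documents do not support that: 14.1.8 does not feed 14.2.4.1, whose key classes hospital supplemental oxygen (item 4) as non-respiratory failure. Nor do they establish that ventilation days will be overstated, since the days variable is undefined rather than defined wrongly.

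**Conclusion.** Both defects hold, as two separate drafting errors of moderate weight. In 14.1.8, following the shell as laid out counts oxygen-only patients in the Mechanical Ventilation row and can add their days. In 14.2.4.1, the adverse-event route read with its footnote can admit shock or multi-organ failure without ventilatory support into a synopsis secondary endpoint.

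Each misclassified patient moves an arm's rate by 10 percentage points, assuming 10 per arm. It would be tempting to add that this could produce a spurious treatment difference, but one or two such patients would not do so against 0/10. The harm is a misreported outcome in a small trial that will be read largely from its counts. How many patients would be affected cannot be judged from the documents.

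**What to change.** **SAP 14.1.8.** Rename the parent row Any respiratory support, show each support on its own row, and list ECMO once. State that the mechanical-ventilation days exclude supplemental and high-flow oxygen. Limit them to invasive ventilation and ECMO only if the case report form identifies invasive ventilation; the form is not among the documents, so the sponsor must check.

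**SAP 14.2.4.1.** Replace the footnote with the synopsis definition and its four named supports. Restrict the adverse-event route to events that required one of them. If shock or multi-organ failure is of interest, report it on a separate row.

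**Protocol.** Reconcile the Synopsis, which includes the respiratory-failure endpoint, with Section 3, which omits it; Section 9.2 points to both for the endpoints.

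**Cost.** The SAP changes are to table shells and footnotes. They need no new data, except that a days variable for invasive ventilation depends on what the case report form recorded. Reconciling the two protocol sections is a wording correction.
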